EUCAST	European Committee on Antimicrobial Susceptibility Testing, European standards for antimicrobial susceptibility testing (http://www.srga.org/Eucastwt/eucastdefinitions.htm)
ICD	International Statistical Classification of Diseases and Related Health Problems, used as discharge diagnostic codes or for coding causes of death. The 9th or 10th revision are currently used in most countries
Impact of a vaccination programme	The measure of the effects of a specific vaccination programme in a specific population, which include indirect, total and overall effect against the target disease
IPD	Invasive pneumococcal disease, defined as isolation of Streptococcus pneumoniae or the detection of Streptococcus pneumoniae nucleic acid or antigen from a normally sterile site
MIC	Minimum inhibitory concentration, a method for antimicrobial susceptibility testing
PCV7	7-valent pneumococcal conjugate vaccine
PCV10	10-valent pneumococcal conjugate vaccine
PCV13	13-valent pneumococcal conjugate vaccine
PPSV23	23-valent pneumococcal polysaccharide vaccine
Sentinel surveillance system	A surveillance system that involves collecting data from a sample of reporting sites
Surveillance/study site (country)	Surveillance system (in a country) that participating to the EU/EEA project. The term "surveillance site" with no other mention refers to a country involved in this ECDC project
Surveillance/study site	Regional surveillance system in a country that are participating to the EU/EEA project and are included in the respective country surveillance site.
Surveillance unit	Hospital/laboratory reporting cases to a surveillance site included in the project
Vaccination coverage	The proportion of the eligible population which is effectively vaccinated. Vaccine coverage should be defined by schedule (number of doses or complete schedule)

Term	Definition
Vaccination registry	Electronic database where vaccination data are recorded. It usually includes patient unique identifier; age; sex; vaccine type; vaccination date; vaccine brand/ manufacturer; vaccine lot number
VE	Vaccine effectiveness, defined as the measure of the direct effect of vaccination against target disease when used under field conditions

1. Introduction

Streptococcus pneumoniae is a Gram-positive diplococcus bacterium causing a wide spectrum of illness either by invading the bloodstream or by mucosal contiguity. Based on capsule polysaccharide composition, more than ninety serotypes of Streptococcus pneumoniae have been identified. These serotypes differ not only in prevalence by area and over time, but also in pathogenicity, clinical presentation and age distribution.

Invasive pneumococcal disease (IPD), defined as the isolation of *Streptococcus pneumoniae* or the detection of nucleic acid or antigen of *Streptococcus pneumoniae* from a normally sterile fluid, may present different clinical conditions such as meningitis, bacteraemic pneumonia, bacteraemia without focus, septic shock, and other less frequent conditions such as arthritis, peritonitis, etc. Transmitted by contiguity to middle ear, sinuses or other locations of the respiratory tract, *Streptococcus pneumoniae* can also cause non-invasive diseases such as acute otitis media, sinusitis or pneumonia. *Streptococcus pneumoniae* nasopharyngeal colonization, particularly in young children, represent the main reservoir of pneumococci and the primary means of transmission to susceptible individuals. As recent acquisition of *Streptococcus pneumoniae* in nasopharynx is thought to precede episodes of pneumococcal disease, carriage plays a key role in the epidemiology of pneumococcus. The pneumococcal carriage is lower in adults without children (estimated 5-10% in the US), but can be higher in the institutionalised individuals¹ Few European studies presented a low carriage rate in the elderly (2.3% in Portugal², 5.3% in Finland, 6% in Dutch elderly with ILI, being dependent on the detection method and type of the sample³).

Two major groups of vaccines are currently available to protect against *Streptococcus pneumoniae*: polysaccharide vaccine (23-valent vaccine - PPSV23) and more recently pneumococcal conjugate vaccines (PCVs). PPSV23, licensed in 1983, is generally recommended for use in the elderly as well as adults and children ≥2 years with underlying medical conditions (risk groups)⁴. Pneumococcal conjugate vaccines⁵ (PCV7, PCV10 and PCV13) covering the 7, 10 and 13 serotypes most frequently causing IPD in developed countries during pre-vaccine era (Table 1), were licensed in the European Union (EU) in 2001 (PCV7), and in 2009 (PCV10 and PCV13) for the use in children under five years old, with PCV10 and PCV13 replacing PCV7. PCV13 was approved for use in adults in 2011, and in children up to 17 years in November 2012. Currently, PCV13 is licensed for prevention of invasive disease, pneumonia and acute otitis media caused by *Streptococcus pneumoniae* in infants, children and adolescents from 6 weeks to 17 years of age, as well as for the prevention

-

¹ Centers for Disease Control and Prevention. Epidemiology and Prevention of Vaccine-Preventable Diseases. Hamborsky J, Kroger A, Wolfe S, eds. 13th ed. Washington D.C. Public Health Foundation, 2015

² Almeida ST, Nunes S, Santos Paulo AC, Valadares I, Martins S2 Breia F, Brito-Avô A, Morais A, de Lencastre H, Sá-Leão R. Low prevalence of pneumococcal carriage and high serotype and genotype diversity among adults over 60 years of age living in Portugal. PLoS One. 2014 Mar 6;9(3):e90974. doi: 10.1371/journal.pone.0090974. eCollection 2014.

³ Palmu AA, Kaijalainen T, Saukkoriipi A, Leinonen M, Kilpi TM Scand J Infect Dis. Nasopharyngeal carriage of Streptococcus pneumoniae and pneumococcal urine antigen test in healthy elderly subjects. 2012 Jun;44(6):433-8. doi: 10.3109/00365548.2011.652162. Epub 2012 Jan 21.

⁴ WHO, 23-valent pneumococcal polysaccharide vaccine WHO position paper – 2008, WER 2008; 83: 373–384

⁵ WHO, Pneumococcal vaccines – WHO position paper -2012, WER 2012; 14; 87:, 129–144

of invasive disease and pneumonia caused by *Streptococcus pneumoniae* in adults \geq 18 years of age and the elderly⁶.

PCV10 and PCV13 were approved on the basis of immunogenicity data. Most EU countries have introduced PCV vaccines in children, but vaccination policies widely vary across member states in terms of vaccine (PCV 10/13), dose schedule (2+1 or 3+1 doses) and target groups (risk groups only or universal vaccination in children). The introduction of the PCV13 vaccination in the elderly is still under evaluation in many EU/European Economic Area (EEA) countries.

Table 1: Streptococcus pneumoniae serotypes included in different vaccines

Vaccine	Serotypes
PCV7	4, 6B, 9V, 14, 18C, 19F, 23F
PCV10	PCV7 serotypes (4, 6B, 9V, 14, 18C, 19F, 23F) and 1, 5, 7F
PCV13	PCV10 serotypes (1, 4, 5, 6B, 7F, 9V, 14, 18C, 19F, 23F) and 3, 6A, 19A
PPSV23	1, 2, 3, 4, 5, 6B, 7F, 8, 9N, 9V, 10A, 11A, 12F, 14, 15B, 17F, 18C, 19A, 19F, 20, 22F, 23F, 33F

1.1 Rationale

A total of 1.6 million deaths due to pneumococcal disease among all ages occur annually worldwide⁷. After the decrease in IPD incidence in children due to PCV introduction, the burden of pneumococcal disease lays now in the elderly.

PCV13 is likely to provide better protection against IPD and pneumococcal pneumonia presenting different immunogenic properties⁸ than PPSV23. CAPITA study was a randomised, double-blind clinical trial including 84,496 elderly ≥65 years in the Netherlands⁹. CAPITA compared PCV13 to placebo for the prevention of a first episode of vaccine-type (VT) Sp CAP (primary objective), first episode of nonbacteriemic/noninvasive VT Sp CAP and a first episode of VT-IPD¹⁰. The PCV13 efficacy for the first episode VT-Sp CAP was 45.56% (95%CI: 21.82%-62.49%, p=0.0006), 45.00% (95%CI: 14.21%-65.31%, p=0.0067) for nonbacteriemic/noninvasive VT SpCAP and 75.00% (95%CI 41.43%-90.78%, p=0.0005) for the first episode of VT-IPD. No efficacy for all cause CAP (5.1%; 95%CI:-5.1 - 14.2) or confirmed deaths

-

⁶ European Medicines Agency. Prevenar 13: EPAR – Product information. Annex I - Summary of product characteristics. 12/05/2015.

⁷ WHO. The global burden of disease: 2004 update. Geneva: World Health Organization; 2008.

⁸ Bonten, M., Bolkenbaas, M., Huijts, S., Webber, C., Gault, S., Gruber, W., and Grobbee, D., 12-3-2014. Community acquired pneumonia immunisation trial in adults (CAPiTA). Pneumonia, volume 3: ISPPD special issue. Page 95.

⁹ Bonten MJ, Huijts SM, Bolkenbaas M, Webber C, Patterson S, Gault S, van Werkhoven CH, van Deursen AM, Sanders EA, Verheij TJ, Patton M, McDonough A, Moradoghli-Haftvani A, Smith H, Mellelieu T, Pride MW, Crowther G, Schmoele-Thoma B, Scott DA, Jansen KU, Lobatto R, Oosterman B, Visser N, Caspers E, Smorenburg A, Emini EA, Gruber WC, Grobbee DE. Polysaccharide conjugate vaccine against pneumococcal pneumonia in adults. N Engl J Med. 2015 Mar 19;372(12):1114-25. doi: 10.1056/NEJMoa1408544.

¹⁰ Pfizer Press Relase March 12, 2014. Available on http://www.pfizer.com/news/press-release/press-release-detail/pfizer_presents_detailed_results_from_landmark_community_acquired_pneumonia_immunization_trial_in_adults_capita_evaluating_efficacy_of_prevenar_13

due to neither VT SpCAP / VT IPD nor confirmed all type SpCAP/All type IPD were reported. However, CAPITA study was not powered to measure neither serotype specific VE nor VE for other outcomes.

Many aspects of PCV13 vaccination in adults still need to be answered:

- No efficacy shown for all cause CAP
 - 5% decline in all cause pneumonia consistent but not significant
- No efficacy shown for mortality
- Efficacy unknown for high risk patients
 - Immunocompromised
 - Institutionalized
 - Very old
- Duration of protection at least about 4 years
 - Need for revaccination?
- Real world effectiveness?
 - How can we distinguish direct PCV13 effects from indirect effects?

PPVS23 is still used in many European countries in the elderly, even though its efficacy against IPD and non-invasive pneumonia is controversial. A meta-analysis on PPSV23 efficacy reported a VE of 74% (OR 0.26, 95% CI: 0.15-0.46, $I^2 = 0$) against IPD, 46% (OR 0.54, 95% CI 0.43 to 0.67, $I^2 = 19$ %) against all-cause pneumonia in low-income countries and 29% (OR 0.71, 95% CI 0.45 to 1.12, $I^2 = 93$ %) in high-income countries¹¹. The latest literature overview that estimated PPSV23 effectiveness for preventing vaccine-type IPD in the 65+ years, suggested an average VE of 60% (range 40%-70%)¹². The PPSV23 effectiveness varied according to immune-competency and decreased after 3-5 years.^{13,14}

Pneumo2¹⁵ survey was conducted under SpIDnet project between July-November 2013 among 30 EU/EAA countries to gather information on IPD surveillance, laboratory capacity and vaccination programmes. None of the 22 countries that filled in a PCV13 questionnaire had introduced the vaccination in adults at that time; however the latest data from ECDC show that seven countries recommend PCV13 in adults¹⁶. Among the 24 countries that filled in a PPSV23 questionnaire in 2013 survey, 10 stated PPSV23 was included in the national immunisation plan and three in the regional immunisation plan. In 12 countries it was recommended by professional associations and in 20 countries the vaccine was on the market. The target population for the PPSV23 vaccination were high risk groups for invasive pneumococcal infection (15 countries), elderly ≥65 years of age (six countries) or ≥60 years of age (one country).

¹¹ Moberley S, Holden J, Tatham DP, Andrews RM. Vaccines for preventing pneumococcal infection in adults. Cochrane Database Syst Rev. 2013 Jan 31;1:CD000422. doi: 10.1002/14651858.CD000422.pub3.

1.2 Study design

This protocol presents a generic approach for conducting vaccine effectiveness studies using the indirect cohort method (also called case only or Broome method) in the elderly. This method was first proposed by Broome et al¹⁷ in early '80s to measure the effectiveness of PPSV vaccines. The design compares the vaccination coverage in IPD/ SpCAP cases due to vaccine serotypes to that of IPD/ SpCAP cases due to non-vaccine serotypes. Therefore, this design may be conducted only with data collected through the IPD/ SpCAP surveillance systems and provides a reliable estimate of vaccine effectiveness. However, this design is not appropriate to measure the VE against all type IPD/SpCAP or all cause CAP, and different designs need to be foreseen to answer questions related to these outcomes.

The design is based on the assumption that the vaccination coverage among the IPD cases due to non-vaccine serotypes is similar to the vaccination coverage in the source population giving rise to the IPD cases due to vaccine serotypes. This may be challenged if the vaccination is associated with a higher or a lower risk of getting non-vaccine serotypes. Two studies in the US¹⁸ and UK¹⁹, evaluated the potential bias introduced by the violation of this assumption when measuring the PCV7 vaccine effectiveness using data from US CDC ABCs and UK IPD surveillance systems in children. The results suggested that the bias that has been attributed to the violation of this assumption is low in the context of observational studies.

Other designs were discussed and proposed in a WHO manual²⁰ published in 2012 to help countries in their efforts to measure the impact of *Streptococcus pneumoniae* and *Haemophilus influenzae* type b conjugate vaccination in children. A prospective matched density case-control study design was proposed as standard. In this study design, cases are identified through the IPD surveillance system and controls are selected among the hospitalised (or outpatient/community) children free of disease at the moment of the case hospitalisation (matching by hospital, age and date of admission). The design was successfully used in the US for measuring PCV7 effectiveness using CDC's ABCs data²¹, and compared with the indirect cohort and screening methods.

Member states are invited to adapt this Generic protocol for PPSV23/PCV13 effectiveness using the indirect cohort method to the local needs and capacities by developing site-specific protocols with the ultimate goal to improve the knowledge on the performance of available vaccines against invasive or non-invasive *Streptococcus pneumoniae* diseases in the elderly.

¹⁷ Broome CV, Facklam RR, Fraser DW. Pneumococcal disease after pneumococcal vaccination. An alternative method to estimate the efficacy of pneumococcal vaccine. N Engl J Med 1980; 303:549:-52

¹⁸ De Serres G, Pilishvili T, Link-Gelles R, Reingold A, Gershman K, Petit S, Farley MM, et al. Use of Surveillance Data to Estimate the Effectiveness of the 7-valent Conjugate Pneumococcal Vaccine in Children Less Than 5 Years of Age over a 9 Year Period. Vaccine 30, no. 27 (June 8, 2012): 4067–4072

¹⁹ Andrews N, Waight PA, Borrow R, Ladhani S, George RC, Slack MPE, Miller E. Using the Indirect Cohort Design to Estimate the Effectiveness of the Seven Valent Pneumococcal Conjugate Vaccine in England and Wales. *PloS One* 6, no. 12 (2011): e28435.

²⁰ WHO, Measuring impact of *Streptococcus pneumoniae* and *Haemophilus influenzae* type b conjugate vaccination, WHO/IVB/12.08, September 2012

²¹ Whitney CG, Pilishvili T, Farley MM, Schaffner W, Craig AS, Lynfield R, Nyquist AC, et al. Effectiveness of Sevenvalent Pneumococcal Conjugate Vaccine against Invasive Pneumococcal Disease: a matched case-control study. *Lancet* 368, no. 9546 (October 28, 2006): 1495–1502.

2. Background of the protocol

The I-MOVE+ programme is a response to the work programme PHC 17 - 2014: "Personalising health and care". "Comparing the effectiveness of existing healthcare interventions in the elderly".

The objectives of the I-MOVE+ consortium are to identify, pilot test, use, and disseminate in and beyond the EU the best study designs to measure the effectiveness and impact of vaccines used in the elderly population to prevent influenza and pneumococcal infections.

As part of I-MOVE+, we will measure the effectiveness of the available (PPSV23) and if it is the case, of the newly introduced vaccine (PCV13) in the elderly population in order to:

- estimate the level of individual protection and its duration against specific and non-specific pneumococcal disease outcomes;
- determine the best data sources to provide evidence for informing public health actions at regional, national and supranational levels.

The following information for the specific study settings should be described in the protocol:

- date of introduction of the vaccine(s): PPSV23 and/or PCV13 in the high risk groups, childhood and all ages vaccinations;
- type(s) of vaccine used and changes over time in the targeted age population;
- vaccination calendar in the elderly;
- target groups for vaccination and potential changes over time;
- estimated PCV and/or PPSV23 vaccination coverage by age group/risks group;
- IPD surveillance system as primary source of IPD related outcomes (i.e. laboratory surveillance, hospital surveillance, primary care surveillance), including serotyping; or hospital discharge data sets as a source for either IPD or pneumonia outcomes.
- sources to document vaccination status;
- sources to document potential confounding factors;
- ethical/ consent requirements.
- ► Each study site to provide a brief description of the specific background for the study site: introduction of vaccine(s), calendar, vaccination coverage, etc.

3. Objectives

3.1 General objective

To measure PPSV23 and/or PCV13 effectiveness against IPD or SpCAP due to vaccine serotypes in the elderly ≥65 years eligible for vaccination in the study site.

3.2 Secondary objectives

To measure the effectiveness of the PPSV23/PCV13:

- By age group among the elderly population, i.e. 65-74, 75–84 and ≥85 years
- By vaccine received: PCV13 or PPSV23 (if PCV13 recommended in the elderly population);
- Against specific vaccine serotypes, including vaccine related serotypes;
- Against different IPD clinical manifestations and SpCAP;
- Against different levels of IPD severity (ICU admission and/or length of hospital stay >14 days and/or presence of septic shock and/or intra-hospital death);
- Against antimicrobial non-susceptibility (by antibiotic tested);
- By time since vaccination.
- ► Each surveillance site to adapt the above objectives to the data sources available in the country/region.

4. Methods

4.1 Study design

Indirect cohort also called case only or Broome method.

4.2 Study setting

The study is embedded in the IPD surveillance system, using the same data sources and database.

- ► Each study site to define the study setting according to the data sources: IPD surveillance system or hospital discharge databases;
- ▶ Description of the surveillance units used to recruit cases: hospitals, laboratories;
- ► Number of participating units, proportion out of the total number of existing institutions (e.g. participating hospitals/ total number of hospitals);
- ▶ Representativeness of the surveillance units reporting IPD or SpCAP cases in the elderly age groups.

4.3 Study population

The study population comprises the elderly ≥65years eligible for vaccination and living in the catchment area of the laboratory/ hospitals participating in the already set up surveillance system, for whom information is collected for surveillance purposes.

► Each study site to define the study population according to the date of PPSV23/PCV13 introduction (if the case), recommendations for vaccination according to age / high risk groups.

4.4 Study period

The study period depends on the date when the PPSV23/PCV13 started to be available for the elderly population in the country/ region or the IPD surveillance system including the targeted age group was set up.

► Each study site to describe the study period: start and end.

TECHNICAL DOCUMENT – Protocol on effectiveness of Pneumo vaccines in elderly

4.5 Outcomes

The primary outcome consists of hospitalised IPD due to any of 13 vaccine serotypes included in the PCV13 or 23 vaccine serotypes included in PPSV23.

Secondary outcomes include:

- Hospitalised IPD cases due to both specific vaccine serotype and vaccine-related serotypes;
- Hospitalised [clinical manifestation] due to vaccine serotypes. In this context, clinical
 manifestation can be: pneumococcal meningitis, bacteraemic/non-bacteraemic pneumococcal
 pneumonia (includes empyema), pneumococcal bacteraemia and others clinical presentations;
- Hospitalised IPD cases of vaccine serotype non-susceptible to antimicrobials;
- Hospitalised severe IPD cases of vaccine serotype.

4.5.1 Case definitions

For the primary outcome, a case is a hospitalised person eligible for PPSV23 and/or PCV13 vaccination confirmed with an IPD according the ECDC case definition (below), in whom serotyping identified a vaccine serotype (PCV13 or PPSV23 IPD/SpCAP cases). The EC 2008 case definition should be used to recruit IPD cases²²:

PNEUMOCOCCAL INVASIVE DISEASE(S) (Streptococcus pneumoniae)

Clinical criteria

Not relevant for surveillance purposes

Laboratory criteria

At least one of the following three:

- Isolation of Streptococcus pneumoniae from a normally sterile site
- Detection of Streptococcus pneumoniae nucleic acid from a normally sterile site
- Detection of Streptococcus pneumoniae antigen from a normally sterile site

Epidemiological criteria

NA

Case classification

A. Possible case

NA

B. Probable case

NA

C. Confirmed case

Any person meeting the laboratory criteria

For secondary outcomes, the case is defined as above for the primary outcome, and in addition:

- A specific vaccine serotype is identified (this can be a vaccine serotype or vaccine related serotype);
- A clinical manifestation is identified as: meningitis, pneumonia, bacteraemia and others;
- Severity is assessed according to: ICU admission and/or length of hospital stay >14 days and/or death within 30 days.

²² European Commission, Commission Decision 2008/426/EC of 28 April 2008 amending Decision 2002/253/EC laying down case definitions for reporting communicable diseases to the Community network under Decision No 2119/98/EC of the European Parliament and of the Council (notified under document number C(2008) 1589)

► Each study site to state the case definitions for each primary and secondary outcome according to data collected.

4.5.2 Reference group

The primary reference group comprises all persons ≥65 years eligible for vaccination, hospitalised for an IPD/SpCAP laboratory confirmed with a serotype identified as non-vaccine serotype (NVT, mainly nonPPSV23 controls) and excluding vaccine related serotypes. Cases with IPD/SpCAP due to vaccine related serotypes will be excluded from the analysis (i.e. serotypes from the same serogroups as the vaccine serotypes for which cross-protection was demonstrated or assumed).

For the secondary outcomes, the reference groups are the following:

- Specific vaccine serotype/ vaccine—related serotypes: NVT-IPD controls, same as for the primary outcome (see above);
- A [clinical manifestation]: NVT controls of the respective [clinical manifestation];
- Antimicrobial susceptibility: NVT controls in which antimicrobial susceptibility is investigated, and MIC provided (EUCAST thresholds will be taken into account for classification);
- Severe IPD cases: NVT-IPD controls admitted in the ICU / a length of hospital stay >14 days.

Matching

Matching can be an option when clustering by age, time or location is observed or the number of VT-IPD cases overpass NVT-IPD cases. For example, when the vaccine serotype IPD cases are clustered in certain age/location/time and NVT in other ages/locations/time, then matching/group matching by age/location/time would be required. Matching by region (or hospital if possible), age and time of hospitalisation (month/years) can be used²³.

► Each study site to describe the selection of the control group (all NVT controls) and matching by different variables (if it is the case) taking into account the outcome used.

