4.5.5 Laboratory methods

To comply with the IPD case definition, laboratory confirmation through culture, PCR or antigen detection could be used for diagnosis in order to allow serotyping. Serotyping is of paramount importance as it is required for IPD cases inclusion and it makes the differentiation between cases and controls.

- Isolation and identification/ PCR could be done at the hospital laboratory or at the reference laboratory
- Serotyping of isolates is usually done at the reference laboratory using capsular reaction testing (Quellung test), PCR or gel diffusion with type-specific antisera
- Antimicrobial susceptibility testing should be done for all isolates for at least the following antimicrobials: penicillin, macrolide, and cephalosporin. MIC will be reported and EUCAST clinical breakpoints used will be used for classification

Specimen collection, transportation and tests used are well defined in case an IPD surveillance system is in place.

For non-invasive SpCAP, the diagnosis can be made using similar tests from non-sterile fluids (sputum, tracheobronchial aspirates, urine, etc.) or the urine antigen testing which allows serotyping.

▶ Each study site to describe how specimens are collected, transported and types of the tests performed for confirmation and serotyping. When confirmation and serotyping was done by PCR, the method and the algorithms used should be described. The sensitivity and specificity of all tests should be provided.

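### The primary control group is worded as IPD/SpCAP in one place and as IPD only elsewhere, and non-invasive SpCAP has no valid case definition

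*Protocol*

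**What the plan says.** **Primary outcome and cases.** Protocol 4.5 states: "The primary outcome consists of hospitalised IPD due to any of 13 vaccine serotypes included in the PCV13 or 23 vaccine serotypes" in PPSV23. Section 4.5.1 requires a primary case to be "confirmed with an IPD according the ECDC case definition (below), in whom serotyping identified a vaccine serotype", and the definition it reproduces demands a normally sterile site. The same sentence then labels these patients "PCV13 or PPSV23 IPD/SpCAP cases".

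**Primary controls.** Section 4.5.2 describes the primary reference group as eligible persons aged 65 or over "hospitalised for an IPD/SpCAP laboratory confirmed with a serotype identified as non-vaccine serotype". Further down, for serotype-specific outcomes, it names "NVT-IPD controls, same as for the primary outcome (see above"). Sections 4.7 and 4.8 speak of NVT-IPD controls only.

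**Exclusions.** Section 4.5.4 has one inclusion sentence covering IPD and SpCAP patients together, followed by two exclusion lists. Only the IPD list bars diagnosis from a non-sterile fluid.

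**SpCAP.** The general objective (3.1) covers IPD or SpCAP, 3.2 lists SpCAP beside the IPD manifestations, and the secondary outcomes in 4.5 include non-bacteraemic pneumococcal pneumonia. Section 4.5.5 says: "For non-invasive SpCAP, the diagnosis can be made using similar tests from non-sterile fluids". Section 4.5.1 says: "For secondary outcomes, the case is defined as above for the primary outcome", with further conditions added to it.

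**The concern.** The indirect cohort method rests on one assumption, stated in 1.2: vaccine coverage among NVT patients stands for coverage in the population that produces the vaccine-type (VT) cases. That is most plausible when cases and controls have the same disease and reach the laboratory by the same route. Section 6.2.6 itself warns that testing depends on presentation and severity. If patients diagnosed from sputum or urine enter as controls while cases must have a sterile-site result, any difference in coverage between the two syndromes passes straight into the odds ratio.

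This is a generic protocol that each site adapts (1.2), and section 8 foresees a pooled article. Two sites could each follow part of the text faithfully and contribute different control groups.

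A second gap follows from 4.5.1. If every secondary case must first meet the IPD definition, pneumonia confirmed only from a non-sterile specimen cannot be a case, although the objectives and outcomes ask for it.

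**Working it through.** **Step 1. The primary pair, section by section.**

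| Section | Cases | Controls |
|---|---|---|
| 4.5 | IPD | not stated |
| 4.5.1 | sterile-site IPD by definition; IPD/SpCAP by label | not stated |
| 4.5.2, opening | not stated | IPD/SpCAP |
| 4.5.2, serotype-specific outcomes | not stated | IPD, said to be the primary controls |
| 4.7, 4.8 | IPD | IPD |

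The opening of 4.5.2 and its own back-reference cannot both describe the primary controls.

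**Step 2. Does 4.5.4 settle it?** Not fully. A patient who enters as an IPD control is excluded if diagnosed from a non-sterile fluid. A patient who enters as a SpCAP control is subject to the other list, which has no such rule. The literal opening of 4.5.2 admits that second patient to the primary reference group.

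**Step 3. Which patients lack a case definition?** Under 4.5.1 a secondary case must have a sterile-site result.
- Bacteraemic pneumonia meets this.
- Empyema confirmed from pleural fluid meets this.
- SpCAP confirmed only from sputum, aspirate or urine does not, although 4.5.5 provides for diagnosing it that way.

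**Step 4. Which reading does Table 4 use?** Its last column counts IPD patients, with vaccine types at 0.6 of the total, so k = 0.4/0.6 controls per case. Its numbers follow from setting the upper 95% limit of the odds ratio at OR + 0.2:

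n(cases) = [1.96 / ln((OR + 0.2)/OR)]² × [1/(p1(1 − p1)) + 1/(k·VC(1 − VC))], with p1 = OR·VC/(1 − VC + OR·VC).

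For coverage VC = 0.5 and VE = 0.5:
- OR = 0.5 and p1 = 0.25/0.75 = 0.333
- bracket = 4.5 + 6 = 10.5
- (1.96/0.3365)² = 33.93
- n = 33.93 × 10.5 = 356.3 cases and 356.3 × 2/3 = 237.5 controls

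The table gives 356 and 238. The formula reproduces 31 of the 32 rows. Restricting the primary controls to IPD therefore changes no planned number.

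**Step 5. What mixing could do (illustration; all inputs assumed).** The protocol gives no coverage by syndrome and no SpCAP share. Let p0 be coverage in NVT-IPD, ps coverage in NVT-SpCAP and w the SpCAP share of controls.

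pm = (1 − w)·p0 + w·ps

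VE read = 1 − (1 − VE) × odds(p0)/odds(pm)

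Take true VE = 50% and p0 = 0.40. Odds in NVT-IPD controls are 0.667, so odds in cases are 0.333.

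| w | ps | pm | odds(pm) | VE read |
|---|---|---|---|---|
| 0.5 | 0.50 | 0.45 | 0.818 | 59% |
| 0.5 | 0.30 | 0.35 | 0.538 | 38% |
| 0.3 | 0.50 | 0.43 | 0.754 | 56% |
| 0.3 | 0.30 | 0.37 | 0.587 | 43% |
| any | 0.40 | 0.40 | 0.667 | 50% |

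A wider grid (p0 = 0.50, ps from 0.40 to 0.60, w from 0.25 to 0.75) gives 32% to 63% for a true VE of 50%, and 59% to 78% for a true VE of 70%. These are crude values, before any covariate adjustment.

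**The case against.** The best defence is that the slash means alternatives, so that IPD is compared with IPD and SpCAP with SpCAP. Much of the text supports this. The slash also sits on the case side in 4.5.1, and 1.2 and 6.2.5 use it for both sides of the comparison. The objective in 3.1 says IPD or SpCAP. Section 4.5.2 already ties controls for each clinical manifestation to that manifestation, and asks sites to choose controls with the outcome in mind. The study sits mainly within IPD surveillance (4.2), where a large SpCAP share is unlikely, although 4.2 also allows discharge databases. Sites must write their own case definitions, and the planned adjustment for age, underlying conditions and functional status could remove part of any bias.

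Most of this stands as evidence of intent. A reader might infer that the protocol plans to compare IPD cases with SpCAP controls; the documents do not support that. They do not remove the contradiction either. Section 4.5 has no primary SpCAP outcome, so the SpCAP half of the primary reference group has no primary cases to pair with. The label in 4.5.1 is attached to a sentence that requires confirmed IPD, which is a second inconsistency. The exclusion that would keep the syndromes apart is written for IPD only.

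A reader might also infer that the SpCAP objective or the non-bacteraemic pneumonia outcome can never have a case. That goes too far: as Step 3 shows, bacteraemic pneumonia and sterile-site-confirmed empyema qualify.

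**Conclusion.** The concern holds as an unresolved contradiction in the definition of the primary comparator, together with a missing case definition for SpCAP confirmed only from non-sterile specimens. It is not a settled plan to mix syndromes. A site following the opening of 4.5.2 to the letter could pool non-invasive SpCAP controls with IPD cases, and the pooled analysis could then combine unlike control groups.

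The effect on VE cannot be sized from the documents. It is zero if coverage is the same in the two syndromes, and it can go either way otherwise. The range of 38% to 59% for a true VE of 50% assumes 40% coverage in NVT-IPD, 30% to 50% in SpCAP, SpCAP forming half the controls, and no adjustment. It shows sensitivity and should not be read as an expected bias. The point still deserves correction before sites adapt the protocol, because it concerns who the primary controls are.

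**What to change.** 1. In 4.5.2, replace IPD/SpCAP with IPD for the primary reference group. State separately that the SpCAP outcome uses NVT-SpCAP controls found by the same tests as the VT-SpCAP cases.
2. In 4.5.1, align the IPD/SpCAP label on the primary cases with the IPD definition it is attached to.
3. In 4.5.1, give non-invasive SpCAP its own case definition, exempt from the sterile-site criterion and consistent with the specimens named in 4.5.5.

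The cost is wording in two sections. Sites that also collect SpCAP may have fewer controls for the primary analysis than a literal reading of 4.5.2 would give them. Table 4 does not change, because it already counts IPD patients only.
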